The clinical study described in this protocol is a safety and efficacy study in order to develop a non-hybrid, fully automated closed loop system that does not require the person to announce meals to the system, and which utilizes the hormone analog pramlintide in combination with insulin to potentially reduce the meal related hyperglycemia and increase the time spent in target range during the daytime.

Primary Objectives:

- To evaluate safety and efficacy of a fixed co-ratio insulin and pramlintide delivery strategy under closed loop control after a meal is detected by the meal detection algorithm
- To evaluate performance of the fully closed-loop system with (1) insulin+pramlintide as compared to (2) insulin-only as measured by incremental area under the curve (iAUC) in the 6 hours following the first meal period

Secondary Objective:

- To evaluate performance of the fully closed-loop system with insulin+pramlintide as compared to insulin-only for other glycemic outcomes

Study Hypothesis:

Our hypothesis is that pramlintide and insulin delivered after a meal by a closed loop system in response to automated meal detection will be well tolerated and will allow for a reduction in the postprandial glucose response as measured by the incremental area under the CGM curve (iAUC) compared with an insulin-only fully closed loop system.

Endpoints***Primary Endpoints:***

- Incremental area under the curve (iAUC) of postprandial glucose as measured by CGM in the 6 hours following the start of first meal. iAUC (mg/dL*min) will be calculated using a trapezoidal method [76], which sums all CGM values in the 6 hour period following the meal above the starting glucose.
- Percent of time with sensed glucose between 70 – 180 mg/dl in the 6 hours following the start of first meal.

Secondary Endpoints

- Incremental area under the curve (iAUC) of postprandial glucose as measured by CGM in the 6 hours following the start of second meal. iAUC (mg/dL*min) will be calculated using a trapezoidal method [76], which sums all CGM values in the 6 hour period following the meal above the starting glucose.
-

- Percent of time with sensed glucose between 70 – 180 mg/dl in the 6 hours following the start of second meal.

(The following secondary outcomes will be measured in the 6 hours following (1) the start of the first meal, (2) the start of the second meal, and (3) full study duration):

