For the three days prior to the pramlintide treatment visit, participants will be instructed to use pramlintide 15 mcg injected subcutaneously via a pen device up to three times daily before each main meal for 1 day then increase to 30mcg before each main meal if tolerating in terms of GI side effects. They will be instructed to initially reduce their usual mealtime insulin doses by 10-20% to accommodate the use of pramlintide, then can increase mealtime insulin dose as needed to target post meal glucose levels <180 or participants preferred post meal glucose levels. The last dose of pramlintide administered at home prior to the treatment visit should be at least 8 hours before the visit.

For participants using basal insulin (such as glargine, Tresiba, or Toujeo insulin) as an evening dose, they will be instructed to take about $1/3 \pm 10\%$ of their usual basal insulin dose as a dose of NPH insulin no later than 7 pm the night before each study visit, and to withhold any basal

insulin on the morning of the study. They will be instructed to bring their home basal insulin to the study visit to take a dose prior to discharge.

For participants using basal insulin as a morning dose, they will be instructed to take usual morning basal insulin dose the day prior to each study visit, and to withhold any basal insulin on the morning of the study. The study investigator will calculate a dose to be given a dose of about $1/3 \pm 10\%$ of their usual basal insulin dose as a dose of NPH insulin prior to discharge from the study visit. They will be instructed to give their home basal insulin the morning after the study visit as they normally do.

For participants using basal insulin as a twice daily dose, they will be instructed to take usual morning basal insulin dose the day prior to each study visit. On the evening before the study visit, they will be instructed to take $2/3 \pm 10\%$ of their usual basal insulin dose as a dose of NPH insulin no later than 7 pm the night before each study visit, and to withhold any basal insulin on the morning of the study. They will be instructed to bring their home basal insulin to the study visit to take a dose prior to discharge.

Insulin Treatment Visit

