Meal detection will be enabled for the study. If iPancreas does not auto-detect the meal after 30 minutes of when they start eating, the study coordinator will assist the participant to enter a meal with a reduction to the amount of carbs entered based on the amount of time since the meal occurred, at the investigator's discretion. Participants will complete a pictorial nausea rating scale for reported nausea at study start and at approximately 6 hours after the first and second meal to report the worse nausea/vomiting they experienced over the prior 6 hours (the Baxter Retching Faces [BARF] scale) (see Protocol Appendix D)[78] and the approximate duration of the nausea.

The MPC closed loop system with the meal detection algorithm can detect if a meal has been eaten, estimate the grams of carbohydrates consumed then dose an insulin bolus based on the estimated grams of carbs, user's carb ratio and estimated time since the meal was consumed. The bolus is delivered automatically. The system reduces the bolus (per calculation below) by 25% as the detection occurs on average 25 minutes after meal is consumed.

$$Bolus(units) = \frac{\text{estimated carbohydrates (g)}}{\text{carb ratio } (\frac{g}{unit})}$$

If CBG >300mg/dL before the lunch meal, then the study will be stopped early and the participant will be given the option to return on a different day for the second meal.

The meal detection algorithm can be enabled or disabled through the insulin profile settings for a given time period. In order to avoid a meal detection before the two scheduled meals, the meal detection algorithm will be disabled through the insulin profile in between the meals.

If stopping criteria for hyperglycemia is reached, the study investigator will calculate a meal bolus with correction dose as in the equation below if no meal bolus was given by the system, otherwise, the investigator will calculate a correction bolus based on current glucose, target

glucose, and correction factor. The final dose that is delivered to the participant will be adjusted if needed by a study investigator considering insulin-on-board, time since meal consumption, and CGM trend. The Omnipod site will be assessed to determine if the insulin should be delivered via the Omnipod, syringe, or via the participant's own insulin pump after it is reconnected.

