An assessment will take place at the beginning of each of the participant's closed-loop studies. We will inquire whether the participant has had changes in their medications and/or medical history to confirm the participant hasn't developed any study exclusion criteria. A CBG will be obtained and measured by a Contour Next glucose meter. When they arrive, participants will be given 15 grams of oral carbohydrate if the CBG reading is less than 70 mg/dl. CBG values > 300 mg/dl will be managed at the discretion of the investigator with a correction bolus and serum ketones will be checked. If serum ketones are >0.6 mM, the study will not be started and insulin therapy will be guided by the onsite investigator. The order of the visits will be randomized.

An Omnipod will be filled with aspart insulin. We will use only name brand insulin, not generic insulin. Additionally, a second Omnipod will be filled with Pramlintide (Symlin, AstraZeneca). The iPancreas system will deliver pramlintide in a fixed ratio to insulin at 6 mcg of pramlintide delivered for every 1 unit of insulin. The Omnipod(s) will be primed and inserted into the skin of the participant's abdomen or flank as directed by the manufacturer. The pods will be placed at least 4 inches apart. If applicable, participants will disconnect his/her own pump and remove his/her own insulin infusion set once insulin delivery has started via the Omnipod(s). If, applicable for participants on multiple daily injection therapy at baseline, we will verify time of last long basal insulin administration. Participants will wear a Polar M600 fitness watch to inform the controller about physical activity. The research staff will initialize the system, input insulin settings and begin the closed-loop study. Two staff will review each of the settings to confirm the settings are entered correctly. Participants will receive training on using the iPancreas smart phone application. A member of the study staff will remain near to the participant for the duration of the study to address any alerts or issues that arise. The study investigator will be on call for the duration of the study.

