The closed-loop study will be stopped and the participant's own pump or basal insulin will be resumed under the guidance of the on call study investigator if any of the following occur after the start of the study: the participant requests that the treatment be stopped, participant pregnancy, one episode of diabetic ketoacidosis as defined as symptoms such as polyuria, polydipsia, nausea, or vomiting, serum ketones > 1.5 mmol/L or moderate/large urine ketones, either arterial blood pH < 7.3 or venous pH < 7.24 or serum bicarbonate < 15 , and treatment

provided in a health care facility including in the absence of hospitalization, severe GI symptoms (i.e. to the point of not being able to tolerate food or liquids or one episode of severe hypoglycemia defined as a hypoglycemic event resulting in altered consciousness requiring another person to actively administer carbohydrate, glucagon, or other resuscitative actions.

Entire study stopping rules

Triggers for reporting unanticipated problems are seizure, hospitalization, death or any other occurrence considered serious by the PI and Medical Monitor. If any studies are stopped for severe hypoglycemia or diabetic ketoacidosis, then the entire study will be halted. Severe hypoglycemia is defined as any event that required the assistance of another person to administer carbohydrate, glucagon, or other resuscitative actions. Diabetic ketoacidosis is classified as: symptoms such as polyuria, polydipsia, nausea, or vomiting, serum ketones >1.5 mmol/L or moderate/large urine ketones, either arterial blood pH <7.3 or venous pH <7.24 or serum bicarbonate <15 , and treatment provided in a health care facility. If an event of severe hypoglycemia or diabetic ketoacidosis should occur, the study will be halted and a description of the serious adverse event and a new risk mitigation plan will be submitted to the FDA. The study will only resume once FDA approval is received. In addition, if there is any unexpected event such as death or patient hospitalization, the studies will be stopped until the root cause is evaluated.

Withdrawal Criteria

The participant may withdraw at will at any time or at the discretion of the Investigator.

A participant must be withdrawn if the following applies:

- Hypoglycemia during the treatment period posing a safety problem as judged by the investigator.
- Hyperglycemia during the treatment period posing a safety problem as judged by the investigator.

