- Protocol deviation having influence on efficacy or safety data as judged by the Investigator.
- Substantial and repeated non-compliance with trial procedures.
- Pregnancy. Intention of becoming pregnant.

Description of the MPC algorithms

Our exercise-aware model predictive control (exMPC) algorithm uses a glucoregulatory model to predict glucose outcomes over a predicted horizon (N_p), and mathematically solve for the optimal insulin doses across the control horizon (N_c) to bring the participant to target. The model is updated at each timestep by a Kalman filter, which uses the difference between CGM observations and model predictions to update the physiologic model states. Exercise is represented by heart rate data collected from a wrist-worn fitness watch. Elevated heart rate is represented by increased glucose disposal in the form of increased insulin sensitivity. In summary, a model-predictive controller uses a physiologic model to calculate how much insulin is required to bring someone to glucose target, and these predictions are adapted to the specific

participant using a Kalman filter. The exMPC algorithm has been described previously and has been clinically evaluated in multiple outpatient studies [79-81].

The Meal Detection feature in the algorithm includes a model for missed meal insulin detection and carbohydrate size estimation[2]. The model includes estimations for carbohydrate consumption based glucose patterns to determine if that person has consumed a meal without announcing it to the system. We refer to this algorithm as the Meal Detection algorithm.

Statistical methods

The primary study endpoints are (1) incremental area under the curve (AUC) of glucose in the 6 hours following unannounced meals and (2) percent of time with glucose sensor 70-180 mg/dL.

The hypothesis to be tested is that pramlintide and insulin delivered after a meal by a closed loop system in response to automated meal detection will improve postprandial glucose control over insulin delivered alone in response to automated meal detection.

Incremental AUC (iAUC) of postprandial glucose (mg/dL*min) will be calculated using a trapezoidal method which sums all CGM values in the 6 hour period following the meal above the starting glucose. (M. M. Tai, "A Mathematical Model for the Determination of Total Area Under Glucose Tolerance and Other Metabolic Curves," Diabetes Care, vol. 17, no. 2, p. 152, 1994, doi: 10.2337/diacare.17.2.152.)

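### Withdrawal is mandatory when the investigator judges that a deviation influenced efficacy data; nothing masks that judgement, and the analysis plan only partly protects the paired comparison.

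*Combined protocol and SAP*

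**What the plan says.** **Withdrawal.** The list under Withdrawal Criteria opens with "A participant must be withdrawn if the following applies". Three of its items matter here, and each rests on the investigator's judgement. Two concern glucose: the item on high glucose reads "Hyperglycemia during the treatment period posing a safety problem as judged by the investigator", and a parallel item covers low glucose. The third concerns trial conduct and reads "Protocol deviation having influence on efficacy or safety data as judged by the Investigator". No list of qualifying deviations, threshold or masked review is given.

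**Knowledge of arm and outcome.** No blinding is described. The Run-in Period section begins "For the three days prior to the pramlintide treatment visit, participants will be instructed to use pramlintide 15 mcg", and no placebo run-in is described for the other visit. The Insulin + Pramlintide Treatment Visit section adds a second pod for pramlintide. Both visit sections describe a cloud server for remote monitoring, with alerts sent to coordinators and investigators.

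**Endpoints.** Both primary endpoints use CGM after breakfast only. They are iAUC over six hours and "Percent of time with sensed glucose between 70 – 180 mg/dl in the 6 hours following the start of first meal".

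**Analysis.** Statistical methods specifies a 2x2 crossover model with a random participant effect. It also names a paired t-test, with a bootstrap of the between-visit difference as the fallback. Observation time is truncated for a participant who leaves early. Multiple imputation from baseline values applies only when more than two participants fail to complete. No analysis set is defined.

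**Stopped visits.** If capillary glucose exceeds 300 mg/dL before lunch, the visit stops and "the participant will be given the option to return on a different day for the second meal" (Meal Description, both visit types). Just before Adverse Events, the protocol also offers an optional repeat of any visit that was stopped prematurely.

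**The concern.** The deviation item makes the perceived effect on the efficacy data a reason to end participation. The person judging can know which treatment was given and can see the glucose trace that becomes the primary endpoint. Whether a participant goes on to the second visit can therefore depend on treatment and response together, after randomisation.

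In a two-visit crossover this matters more than in a parallel trial. A participant withdrawn after visit 1 has no second value, so their within-person contrast is gone. If such losses fall mostly on poor responses under one treatment, the estimated difference moves in that treatment's favour. If they are unrelated to treatment, only precision suffers.

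**Working it through.** **1. Reproduce the stated power.** Inputs from Power Analysis: n = 35 pairs, standardised paired differences of 0.56 and 0.49, two-sided alpha 0.05, paired t-test. Power is P(T > t_crit), where T is noncentral t with n − 1 degrees of freedom and noncentrality d√n. The other tail is negligible.

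- d = 0.56: noncentrality 0.56 × √35 = 3.313, critical value 2.032, power 89.6% (stated 90%).
- d = 0.49: noncentrality 0.49 × √35 = 2.899, same critical value, power 80.4% (stated 80%).

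The plan's figures hold.

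**2. When is a paired primary value lost?** The answer depends on when withdrawal occurs.

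| Withdrawal occurs | Paired primary value |
|---|---|
| During or after visit 1, before visit 2 | Lost: no visit-2 value |
| At visit 2, within six hours of breakfast | Incomplete: visit-2 window truncated |
| At visit 2, after that window | Both values already observed |

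**3. What does the analysis plan recover?**

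- The paired t-test and the bootstrap of the between-visit difference need both visits.
- The mixed model can use a single visit, but that visit says little about the within-person contrast. The model's validity also requires that the loss be explained by observed data.
- With one or two non-completers no imputation is planned. Above two it is, but from baseline values, not from the post-meal glucose that may have prompted the withdrawal.
- Truncation shortens a window; it does not supply a missing visit.

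**4. Precision alone.** The number of losses is an assumption, because the documents give no withdrawal rate. Two losses are the most that occur before imputation is planned. Study Population and Subject Recruiting both give 35, as completer target and enrolment goal, with no dropout allowance stated.

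| Complete pairs | Power at 0.56 SD | Power at 0.49 SD |
|---|---|---|
| 35 | 89.6% | 80.4% |
| 34 | 88.7% | 79.2% |
| 33 | 87.7% | 77.9% |

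**5. Selection.** A pair lost after visit 1 can be selected only on visit-1 data, so the simulation selects on that. Assumptions: 35 participants split as evenly as possible between sequences, no true effect, within-person correlation 0.5 (so the SD of the difference equals the SD of a single visit), and a complete-case paired t-test.

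| Pairs lost | Worst visit-1 results, pramlintide-first only: shift | Type I error | Worst visit-1 results, either arm: type I error |
|---|---|---|---|
| 1 | 0.03 SD | about 5.6% | about 5% |
| 2 | 0.05 SD | about 6.1% | about 5% |
| 3 | 0.07 SD | about 6.8% | about 5% |

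The one-arm shifts favour pramlintide. Selecting only insulin-first participants would reverse the sign. The last row exceeds the imputation threshold, so it describes a complete-case analysis, not the planned one.

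**The case against.** The strongest reply is that Withdrawal Criteria governs participation, not analysis. A reader might infer that withdrawn participants' pairs are thrown away. The documents do not say so: they truncate observation time for early leavers, fit a random participant effect, plan imputation above two non-completers, and allow a stopped visit to be repeated. This stands, and it limits the point to pairs that *can* be lost. It does not remove the point, because no text says the data are kept and step 3 shows that each safeguard is partial.

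Second, the hypo- and hyperglycaemia items are ordinary safety rules, limited to events judged to be a safety problem. That stands, and they are not criticised as such. A reader might also see a flat contradiction between the hyperglycaemia item and the offer to return after a pre-lunch reading above 300 mg/dL. The text does not support that: a visit-level threshold and a participant-level safety judgement can coexist, and lunch falls at about the end of the primary window. What remains is an unclear boundary between stopping a visit and leaving the trial.

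Third, a reader might delete the one, two or three least favourable between-visit differences and obtain error rates of about 8%, 13% and 21%. Those rates require both visits to have been observed, at which point both primary values exist, and removal always against the same arm. They do not describe loss after visit 1.

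Finally, if the completer target means that withdrawn participants are replaced, the power loss disappears. No replacement rule is stated, and replacement would not undo selection.

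**Conclusion.** The point holds in a limited form. The protocol requires withdrawal on a non-safety judgement about efficacy data, by someone who can know arm and outcome, and the analysis plan does not fully protect the paired comparison. That the investigator knows the arm is an inference from the second pod, the one-sided run-in and the absence of any blinding text; it is not stated.

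The likely effect is small. Two lost pairs cost about 2 to 2.5 points of power. One-arm selection of one to three visit-1 results shifts the estimate by 0.03 to 0.07 SD and gives a type I error of about 5.6% to 6.8%; selection regardless of arm leaves it at about 5%. These figures rest on assumed numbers of losses, a correlation of 0.5 and a complete-case test. The documents fix neither the size nor the direction of any bias. The change is worth making because it is cheap and closes a route to outcome-dependent loss.

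**What to change.** 1. Remove influence on efficacy data as a ground for mandatory withdrawal. State that a protocol deviation is recorded and does not by itself end participation or exclude data.
2. State in Statistical methods that all observed CGM data from randomised participants enter the primary comparison. The mixed model then has to carry the primary test, because the paired t-test cannot use a single visit.
3. Make any per-protocol analysis supplementary, with exclusions decided by someone masked to visit treatment and CGM outcome.
4. Separately, reconcile the hypo- and hyperglycaemia withdrawal items with the return and repeat-visit provisions, so that stopping a visit and leaving the trial are distinguished. No clinical rule is proposed here.

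The cost is amendment wording and a little extra analysis. The downside is that some deviating visits stay in the primary analysis and add noise.

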- Net area under the curve (netAUC) of postprandial glucose as measured by CGM in the 6 hours following the start of first meal. netAUC (mg/dL*min) will be calculated using a trapezoidal method [76], which sums all CGM values in the 6 hour period following the meal above the starting glucose and subtracts CGM values below the starting glucose.
- Percent of time with sensed glucose <70 mg/dl
- Percent of time with sensed glucose between 70 – 140 mg/dl
- Mean sensed glucose
- Percent of time with sensed glucose <54 mg/dl
- Percent of time with sensed glucose >180 mg/dl
- Percent of time with sensed glucose >250 mg/dl
- Mean amount of insulin delivered (in units and units/kg)
- Mean amount of pramlintide delivered (in mcg and mcg/kg)
- Coefficient of variation
- LBGI
- HBGI
- Safety endpoints (over full study duration):
 - Adverse events
 - Number of adverse events probably or possibly associated with pramlintide administration (see ‘Causality Relationship’ below)
 - Baxter Retching Faces (BARF)/VAS scale for gastrointestinal issues after first and second meal, see Protocol Appendix D.
 - Mean duration of gastrointestinal issues after first and second meal as reported by participant on BARF/VAS scale, see Protocol Appendix D.
 - Episodes of carbohydrate intake to treat hypoglycemia (defined as 15g carbohydrate intake)
 - Episodes of hypoglycemia defined as CGM <70mg/dL for 10 minutes or more
 - Number of provider-administered insulin injections due to hyperglycemia

Study Type

This is a single-center, crossover trial designed to evaluate glucose outcomes of a fully closed-loop system with insulin+pramlintide dosed in response to meal detection as compared to an insulin alone fully closed loop system.

Study Population

Study population will be adults with type 1 diabetes, ages 18 – 70 years of age. Younger participants are excluded as it is appropriate to assess safety first in the over 18 year old population. We are targeting a total of 35 participants to complete the full study protocol.

[figure not shown]
Power Analysis

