A sample size of 35 participants provides 90% power to detect a standardized paired mean difference of 0.56 SD, or 80% power to detect a 0.49-SD difference with a two-sided test at the .05 level of significance. This is calculated using a paired t test to approximate a mixed model with treatment, period, and sequence effects. Data from a previous study [24] showed a 0.64-SD reduction with pramlintide in 4-hour postprandial AUC for participants with >40 U bolus insulin per day. We plan to recruit more than half of our study participants from this population and so we expect to observe a slightly smaller reduction in AUC.

Protocol Summary:

Participants will undergo two study visits to evaluate (1) insulin+pramlintide versus (2) insulin-only delivery strategies. The order of the visits will be randomized. Meal scenarios will be identical across all study arms. Participants will arrive at approximately 7:30 am for all visits, be monitored through the afternoon and discharged at approximately 8 pm. During each study visit, participants will wear Omnipod(s) to deliver insulin and/or pramlintide and a Dexcom G6 CGM to measure glucose and a Polar M600 to measure activity levels. See Figure 1 and 2 below.

Figure 1: Study flow diagram

Time	Activity	Hours post meal
7:30 AM	Begin closed loop study	0
8 AM	Breakfast	1
9 AM		2
10 AM		3
11 AM		4
12 PM		5
1 PM		6
2 PM	Lunch	1
3 PM		2
4 PM		3
5 PM		4
6 PM		5
7 PM		6
8 PM	Discharge	

Figure 2: Treatment visit timeline

Subject Criteria

Inclusion Criteria:

1. Diagnosis of type 1 diabetes mellitus for at least 1 year.
2. Participants 18 to 70 years of age.
3. Current use of an insulin pump for at least 3 months with stable insulin pump settings for >2 weeks. OR Current use of multiple day injection insulin therapy with stable doses for >2 weeks.
4. Uses a carbohydrate ratio, at least occasionally, to dose meal time insulin
5. HbA1c \leq 10.5% at screening.
6. Total daily insulin requirement is less than 139 units/day.
7. Willingness to follow all study procedures, including attending all clinic visits.
8. Willingness to sign informed consent and HIPAA documents.

Exclusion Criteria:

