We will estimate the difference between systems using a fixed effect in a standard 2x2 crossover model with a random participant effect. We will also control for sequence (AB or BA) and period (1 or 2), though we do not anticipate statistically significant effects for these parameters.

We anticipate that the primary outcomes will be approximately normally distributed. We will review the appropriateness of this assumption using both goodness-of-fit tests and diagnostic plots, such as quantile-normal plots. If the normality assumption holds, possibly with a transformation of the outcome, we will test the difference between the study arms using a paired t-test. In the case of mild departures from normality or unequal variances at the two time points, we will re-analyze the primary outcome as the difference between the two visits using bootstrapped standard errors, which avoid distributional assumptions. We will use two-sided tests at the 0.05 level of significance.

Missing data: Missing sensed glucose values will be interpolated for up to 30 min segments. Longer periods of missing data will be omitted if they represent <3% of observation time (which will be truncated if a participant leaves the study early). If the missing data are >3% of observation time, we will use available CBG values to interpolate or impute using measurements. In the case that >2 participants fail to complete the study, we will analyze the primary outcome under multiple imputation using baseline values.

Confidentiality and Protection of Human Subjects

RISKS and BENEFITS

Risks: The risks of the protocol procedures are considered minor. Nonetheless, since pumps and sensors used within automated glucose control systems are imperfect, there is a risk for hyperglycemia and hypoglycemia. All studies will have frequent glucose and ketone samplings and a member of the study staff will be present for studies with a study investigator on call at all times.

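### First-meal iAUC is not adjusted for the visit's starting glucose, which may leave precision unused; second-meal iAUC is anchored to a post-treatment value and can mislead

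*Combined protocol and SAP*

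**What the plan says.** The Endpoints section and Statistical methods define iAUC by a trapezoidal rule that "sums all CGM values in the 6 hour period following the meal above the starting glucose". Neither says which CGM reading, or what average of readings, is the starting glucose. First-meal iAUC is a primary endpoint. The same quantity "in the 6 hours following the start of second meal" is secondary, and netAUC uses the same kind of anchor.

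Statistical methods gives the model: "We will estimate the difference between systems using a fixed effect in a standard 2x2 crossover model with a random participant effect". Sequence and period are added. A paired t-test, or a bootstrap of the visit difference, follows. Baseline values appear only in the rule for multiple imputation.

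The Power Analysis states: "A sample size of 35 participants provides 90% power to detect a standardized paired mean difference of 0.56 SD". Its second figure is 0.49 SD at 80% power, again two-sided at 0.05. On method it says: "This is calculated using a paired t test to approximate a mixed model with treatment, period, and sequence effects".

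Both treatment-visit sections bound the pre-breakfast glucose in the same way. Action is taken at 2 am above 150 or below 100 mg/dL, and on arrival below 70 or above 300 mg/dL. Closed loop starts at about 7:30 and breakfast is at about 8. Lunch follows about six hours later on the same system, and only a CBG above 300 mg/dL stops the visit before it. The Run-in Period (three days of pramlintide) precedes only the pramlintide visit.

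**The concern.** Area above a starting value depends on that value as well as on the meal response. If the closed loop pulls glucose back toward a target, a high start shrinks the area and a low start enlarges it.

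At breakfast, a start that differs between a participant's two visits therefore adds noise to the paired difference. The value is already recorded and could be used to remove that noise.

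At lunch the issue is interpretation. The start is itself a result of six hours on the assigned system. An arm that controls breakfast better may begin lunch lower, be measured from a lower line and show a larger lunch iAUC. The reverse can also happen. netAUC does not guard against this, because it moves with the same anchor.

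**Working it through.** **1. The plan's own power.** Inputs from the Power Analysis: n = 35 pairs, two-sided 0.05, effects of 0.56 and 0.49 SD of the paired difference. Power = P(T > t(0.975, 34)), with T noncentral t on 34 df and noncentrality d√35. This gives 89.6% at 0.56 SD and 80.4% at 0.49 SD. Both stated figures reproduce.

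**2. How far the start moves iAUC.** Suppose the start changes by δ.
- If the whole curve shifts in parallel, iAUC does not change.
- If the later curve is unchanged and stays above the start throughout, iAUC moves by δ × 360 min. For 10 mg/dL that is 3,600 mg/dL*min, the upper limit.
- If the disturbance decays as exp(−t/150) (assumed) and the curve stays above the start, the change is δ × [360 − 150(1 − e^(−2.4))] = 10 × 223.6 = 2,236 for 10 mg/dL.

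The correlation between the two between-visit differences thus depends on loop behaviour that the documents do not quantify. In simulation it is about zero under a parallel shift, and −0.44 to −0.80 when the loop returns glucose toward target. The within-person start SDs behind such figures are assumptions.

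**3. First-meal power with adjustment.** Let ρ be the size of that correlation. Adjustment multiplies the SD of the paired difference by √(1 − ρ²). Noncentrality becomes d√35/√(1 − ρ²), with 35 − 3 = 32 df (mean, period, covariate).

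| ρ (assumed) | Power at 0.49 SD | Power at 0.56 SD | Equivalent unadjusted n = 35/(1 − ρ²) |
|---|---|---|---|
| 0 | 80.3% | 89.5% | 35.0 |
| 0.2 | 81.8% | 90.6% | 36.5 |
| 0.3 | 83.8% | 92.0% | 38.5 |
| 0.4 | 86.6% | 93.9% | 41.7 |
| 0.5 | 90.1% | 96.0% | 46.7 |
| 0.6 | 94.0% | 98.0% | 54.7 |

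At ρ = 0 the loss at 0.49 SD is 80.4 − 80.3 = 0.1 percentage points.

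**4. Lunch sign reversal.** Assumed curve: G(t) = 120 + (start − 120)·exp(−t/150) + A·(t/90)·exp(1 − t/90), read every 5 minutes for 360 minutes. The control arm starts at 150 mg/dL with A = 100, giving iAUC 15,644 and mean 192.4 mg/dL. The treated arm has a 10% smaller meal excursion (A = 90).

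| Treated start (mg/dL) | iAUC difference | Mean glucose difference (mg/dL) |
|---|---|---|
| 150 | −2,124 (−14%) | −6.1 |
| 140 | −120 (−1%) | −9.9 |
| 130 | +2,115 (+14%) | −13.7 |
| 120 | +4,351 (+28%) | −17.5 |

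With equal starts iAUC shows the benefit. With a start 10 mg/dL lower it shows almost none. At 20 mg/dL lower the sign is wrong, although excursion and mean are both lower. With a 20% smaller excursion, the sign changes between starts of 130 (−106) and 120 (+2,130).

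netAUC does not help: at a start of 130 its difference is +2,250. Removing the anchor shift gives the difference in total AUC, 2,250 − 20 × 360 = −4,950, which has the right sign.

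The distortion can also flatter an arm. A treated start of 170 with no change in the meal effect gives iAUC −3,295 (−21%) while mean glucose is 7.6 mg/dL higher.

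**The case against.** **The start is controlled.** A reader might call it uncontrolled. It is not: the same 2 am and arrival rules apply before both visits, and closed loop begins before breakfast. Those rules leave a wide range, so loosely bounded is the accurate description.

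**The stated power is right.** It is expressed in SDs of the paired difference, so noise from the start is already inside that SD. Randomised visit order balances chance differences in the start. This stands: for breakfast the point concerns efficiency, and the gain rests on an unknown correlation.

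**Run-in bias.** Because the run-in precedes only the pramlintide visit, one might infer a biased start. The documents show neither size nor direction. They also let mealtime insulin rise again after the initial reduction, and place the last home pramlintide dose at least 8 hours before the visit. Bias is a possibility, not a finding. The same asymmetry cuts against adjustment, since conditioning on a start that the run-in had shifted could remove part of the strategy's effect. That is why the unadjusted result should stay in view.

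**Lunch is secondary and cross-checked.** Time in range and mean glucose are prespecified for the same six hours, so a misleading lunch iAUC would probably be noticed. This lowers the stakes. It does not tell a reader which result to believe when they disagree. Statistical methods speaks of unannounced meals without naming the first, which could suggest that lunch is part of the primary endpoint. The Primary Objectives and Endpoints sections limit primary iAUC to the first meal, so I treat lunch as secondary.

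**Conclusion.** The point holds, at moderate weight.

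- **First meal (primary).** The model omits an available covariate tied to the endpoint's definition. The likely benefit is power of 84-94% instead of 80% at 0.49 SD if ρ is 0.3 to 0.6. It is small at 0.2 (81.8%), and the cost at zero is negligible. The sample size calculation is not in error.
- **Second meal (secondary).** The anchor is post-treatment by design. Sign reversal is arithmetically possible with a start about 20 mg/dL lower and a truly smaller excursion. This rests on assumed curves. The documents give no size or direction for a pre-lunch difference, so they do not show that reversal will occur in this trial.

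A reader might extend the argument to the primary time-in-range model. That endpoint is not measured from the starting glucose, and nothing here shows that its model needs the covariate.

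**What to change.** **First meal.** State which CGM reading, or average of readings, is the starting glucose. Add the visit's pre-breakfast value, centred on the participant's two-visit mean, to the iAUC crossover model. Carry it into the paired test and the bootstrap by regressing the visit difference in iAUC on the visit difference in start. Report the unadjusted result as a sensitivity analysis, because the run-in precedes only one visit.

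**Second meal.** Do not adjust for the lunch start, which is post-treatment. Either anchor lunch iAUC to that visit's pre-breakfast glucose, or base the comparison on total AUC or mean glucose adjusted for pre-breakfast glucose. Re-anchoring changes what is estimated, so the text should say so. Interpret lunch-anchored iAUC and netAUC only alongside that result. State which value is the anchor when a second meal is taken on a different day, as the Meal Description allows.

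**Cost.** Analysis wording, fixed before results by arm are seen, and one degree of freedom. The CGM values are already collected, and visit procedures do not change.
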